General aim and endpoint: To assess study feasibility and provide estimated effect sizes (point estimates with confidence intervals) for all measures of interest in order to plan an adequately powered study. We will assess recruitment rates and acceptability of treatment in arms involving exclusive enteral nutrition.

Primary outcome and endpoint: To assess the efficacy of 6 weeks of ECS in inducing remission (CDAI <150) compared to treatment with CS in adult patients with active CD (CDAI >220 and either CRP >5 or fecal calprotectin >250 mg/l).

Secondary outcomes and endpoints: To determine the beneficial effect of 6 weeks of ECS as compared to CS in inducing:

1. Clinical disease improvement (drop in CDAI >70 or 100)
2. Improvement in quality of life (using the Inflammatory Bowel Disease Questionnaire (increase IBDQ scores))
3. Biochemical remission (normalization of either serum CRP and/or fecal calprotectin)
4. Changes in microbiota composition (16S sequencing Illumina)
5. Normalization of colonic transit (SHAPE 0-5 markers at day 5)³⁴ among those with altered transit at baseline
6. Decrease in anxiety and/or depression scores (decrease >2 points HAD-A and/or HAD-D scores)
7. Increase in body weight and improvement in nutritional status (increased levels of micronutrients)
8. Decrease of indirect markers of mucosal integrity (IFABP2)
9. Changes in bacterial fermentation profile (SCFAs: acetate (acetic acid), propionate (propionic acid), and butyrate (butyric acid))^{26,27}.
10. Decreased number of adverse events

METHODS

Study design

Protocol date: October 2018

Randomized control trial; 3 arms of treatment: EEN plus standard or short course of CS (ECS, ECSC) vs CS alone (CS) conducted at McMaster University Medical Centre (Figure 1). The study will last 10 weeks and will involve 4 visits. At the screening visit, we will assess clinical history and symptoms, perform a physical exam and complete bloodwork after the informed consent is signed. Randomization will occur at the second visit (pre-treatment), when the inclusion and exclusion criteria and symptoms will be re-assessed, and baseline stool and urine samples will be collected. In addition, we will perform a SHAPE study and patients will be assessed by a dietitian or clinical nutrition support specialist to assess dietary factors and estimate energy needs using the Harris Benedict equation as detailed below.

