Patients will be instructed to take the allocated treatment and to collect empty bottles/blisters of medication to assess the compliance at the next visit. Six weeks later (visit 3), their symptoms will be re-assessed, blood, urine and stool samples collected and SHAPE study performed. Patients will be instructed to stop the EEN or decrease the dose of CS, as detailed in the section “Follow up after treatment”. In the last visit (4th visit; 10 weeks after enrollment) we will collect information on symptoms, stool samples and urine.

The study protocol will be submitted by the investigator for approval by the Hamilton Integrated Research Ethics Board (HiREB).

Randomization process

The sequence of the treatments will be randomly generated using a computer-based pseudo-random number generator (RStudio Team (2015). RStudio: Integrated Development for R. RStudio, Inc., Boston, MA) Patients will receive one of challenges A,

B, or C consisting of CS, ECS or ECSC. A third person not involved in the study will perform the randomization to preserve treatment allocation concealed from participants and study staff. A block randomization will stratify patients by disease location (colonic/small bowel involvement). Each treatment will be assigned a number according to the randomization sequence. On recruitment, the patient will be assigned into one of three strata and given the next consecutive randomization number available for that stratum. Treatment will be not blinded for patients or study staff.

Subject recruitment

Subjects will be recruited from McMaster University Medical Centre (MUMC) Digestive Diseases Clinic, identified in an ongoing database organized in 2008 and by recruitment flyers posted at McMaster University Medical Centre, Juravinski Hospital and Hamilton General Hospital. Patients in the database signed an informed consent agreeing to be contacted for future research. Patients will be contacted by study personnel and invited to participate in the study.

After the subject has provided written consent to participate, an inclusion checklist will be completed. Subjects will be enrolled after having fulfilled all inclusion criteria, and none of the exclusion criteria.

Participants

One hundred adult patients diagnosed with IBD will be recruited at McMaster University Medical Centre. This will provide 30 subjects in each treatment arm, allowing for 10% dropout rate.

Inclusion criteria:

1. Adult patients (age 18-75 years)

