2. Confirmed CD diagnosis for at least 6 months
3. Clinically active disease (CDAI >220 or HBI>6) or evidence of activity in endoscopy
4. Biochemical evidence of disease activity (CRP > 5 and/or fecal calprotectin > 250),

Exclusion criteria:

1. Current treatment with EEN
2. Intestinal obstruction, perforation, toxic megacolon, massive gastrointestinal bleeding, abdominal abscess, or other criteria considered by the investigator which preclude the use of EEN;
3. Stricture disease
4. Previous intestinal resection with a remnant bowel <180 cm
5. Treatment with prednisone in last 30 days;
6. New start or change in dose of azathioprine, 6-mercaptopurine, cyclosporine, other immunosuppressant or biologics in the last 90 days. Doses of these medications must also remain unchanged for the duration of the study.
7. New start or change in dose of 5ASA in last 30 days. 5ASA dose must remain unchanged for the duration of the study.
8. Treatment with antibiotics or probiotics use in the last 30 days.
9. Pregnancy or lactation
10. Any serious illness considered by the investigator that will interfere with the study procedure or results.

Intervention

Participants will be randomized to one of the following interventions:

1. Exclusive enteral nutrition plus corticosteroids

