Following the completion of the period of exclusive enteral feeding, patients receiving EEN will be instructed to gradually reintroduce foods by adding one individual item every 2 days as shown in Table 1 ^{32,33} and Appendix with instructions for food introduction with coincident reduction of formula volumes under the supervision of an expert in Nutrition. The accelerated introduction of foods was based on a recent study showing similar results with additional benefits of 2 days vs 4 days ³³.

Treatment compliance

The subjects will be asked to keep the cans of Modulen and blister packs of prednisone during the entire treatment period and bring them back to the investigator at the end of that period. Compliance will be recorded in the CRF. In order to improve assessment of patient's compliance, 2 copies of a paper sheet diary will be provided at Visit 1. Patients

consuming <80% of the prescribed treatment dose throughout the study, or those who interrupted therapy for more than three consecutive days will be considered as noncompliant.

Measurements before and after treatment

- Clinical data regarding demographics, disease location and activity (Harvey-Bradshaw Index), social life and habits, past and current clinical medical background, previous surgeries, nutritional status (malnourishment, weight/ height) will be collected in CRF.
- Dietitian/ Certified nutrition support clinician: Dietary habits and caloric intake will be recorded at baseline with nutritional assessment during visits
- Bloodwork to assess for inflammatory markers, CRP, fecal calprotectin, ESR, as well as CBC, platelets, micronutrients (albumin, vitamin D, B12, A, zinc, copper, chromium)
- Questionnaires: McMaster Food frequency questionnaire(Hamilton, ON), quality of life (SIBDQOL¹³), disease activity (CDAI), anxiety and depression (HAD score, Beck inventory), and nutritional assessment (Subjective Global Assessment¹⁴ Braun Nutriscreen program)
- Gastrointestinal transit (colonic transit: SHAPE study and orocecal transit^{24,25}: patient will take one capsule and have an x ray on day five, following R.C. Evans, et al protocol, where ≥ 6 markers indicate delayed transit, therefore ≤ 5 is normalization of colonic transit).³⁴
- Stool sample (frozen samples) for microbiota composition (16S sequencing Illumina; Dr. [name]'s lab) metabolomics and metagenomics ([name]?)¹⁵

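### Secondary outcome 3 reduces CRP and calprotectin to an undefined yes/no on one week-6 sample; a baseline-adjusted log-scale comparison would give a more precise effect size for planning

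*Combined protocol and SAP*

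**What the plan says.** Item 3 of the secondary outcomes, compared between ECS and CS after six weeks, is "Biochemical remission (normalization of either serum CRP and/or fecal calprotectin". No normal limit, minimum fall or repeat sample is attached to it.

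Inclusion criterion 4 is "Biochemical evidence of disease activity (CRP > 5 and/or fecal calprotectin > 250", and the primary outcome repeats it as "either CRP >5 or fecal calprotectin >250 mg/l". One raised marker is enough for entry. These are the only limits given for the two markers.

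Under Study design, screening staff "perform a physical exam and complete bloodwork after the informed consent is signed". Visit 2 adds baseline stool and urine. Then: "Six weeks later (visit 3), their symptoms will be re-assessed, blood, urine and stool samples collected and SHAPE study performed". At the last visit "we will collect information on symptoms, stool samples and urine", with no blood. The screening blood is therefore the only scheduled pre-treatment CRP, visit 3 gives the only later one, and no later stool result is tied to the endpoint.

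Item 5 (colonic transit) is specified more fully. It applies only to patients "among those with altered transit at baseline", and the measurements section gives its limit: "markers indicate delayed transit, therefore ≤ 5 is normalization of colonic transit". Item 3 has neither feature.

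The general aim is to provide point estimates with confidence intervals for all measures, for planning a larger trial. The statistical analysis section offers descriptive summaries, t or Mann-Whitney tests, and a logistic regression linking response to microbiota. It mentions no baseline adjustment.

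**The concern.** Patients enter because a marker is above a line. If remission means being at or below the same line on one later sample, a CRP going from 5.5 to 4.9 or a calprotectin from 260 to 245 is a success, while a calprotectin falling from 1500 to 300 is a failure. Some crossings will be ordinary fluctuation, helped by regression to the mean because the entry value was selected for being high. The and/or wording, at entry and in the endpoint, leaves a further gap: a patient who enters on one marker may count as in remission through the other, which was never raised.

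At stake is the quality of the effect size handed to the full trial. A yes/no reading of two continuous markers discards most of the information in samples that will be collected anyway.

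**Working it through.** **The plan's own figure.** The documents give no rate, variability or false-responder share for this endpoint. The related figure is the sample size: 3 × 30 = 90, and 90/0.9 = 100, which reproduces the stated 100. It is a pilot rule, not a power calculation.

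**Step 1: one patient, no true change.** Assumption: log-normal marker with within-patient coefficient of variation CV, so log SD s = √ln(1 + CV²). For a patient observed at r times the limit at entry, ignoring selection, the chance of being at or below it on the second sample is Φ(−ln r / (s√2)). With CV 0.5, s = √ln 1.25 = 0.472 and s√2 = 0.668.
- r = 1.5: Φ(−0.405/0.668) = 27%
- r = 2: Φ(−0.693/0.668) = 15%
- r = 3: Φ(−1.099/0.668) = 5%

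If the intended normal limit were half the entry cut-off, the r = 1.5 patient would be at 3 times that limit, and 27% becomes 5%. The size of the problem therefore depends on a limit the protocol does not state.

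**Step 2: a trial population, no true change.** Assumptions, none from the documents: median CRP 8-20 and calprotectin 300-800 before selection, between-patient log SD 1.0, correlation 0.4, within-patient log SD 0.3-0.7, entry if CRP >5 or calprotectin >250, and normal limit equal to the entry cut-off. By simulation, a marker raised at entry crosses back in about 6-30% of patients (17% at medians 12 and 500, log SD 0.5). A second assumed grid (medians 1.5-4 times the cut-off, CV 0.3-0.8, correlation 0.3 or 0.6) gave 5-29%. Read literally, with any marker normal at week 6 counting, that grid gives 13-51%, almost all because one marker was already normal at entry (12-49% of patients).

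**Step 3: with a real effect.** Assumptions: calprotectin only, median 500 before selection, raised at entry, true falls of 65% (ECS) and 40% (CS), between-patient SD of response 0.6 on the log scale. CS is ECS minus the difference.

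| Within-patient log SD | ECS | CS | Difference (points) |
|---|---|---|---|
| 0 | 50.1% | 27.8% | 22.3 |
| 0.3 | 49.6% | 28.8% | 20.8 |
| 0.5 | 49.4% | 30.5% | 18.9 |
| 0.7 | 49.5% | 32.6% | 16.9 |

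The loss is 22.3 − 20.8 = 1.5 to 22.3 − 16.9 = 5.4 points. The 95% half-width at 30 per arm in the no-noise row is 1.96 × √(0.501×0.499/30 + 0.278×0.722/30) = 24.0 points.

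**Step 4: cost of dichotomising.** Same scenario, medians 500-800, log SD 0.3-0.7, 30 per arm, two-sided 5%. The true ratio of geometric means is 0.35/0.60 = 0.58.

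| Comparison at week 6 | Power, about |
|---|---|
| Normalized yes/no | 25-39% |
| Log value, unadjusted | 38-54% |
| Log value, adjusted for own baseline log value | 48-82% |

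Repeat simulations move the ends by a point or two. Without measurement noise, the yes/no comparison still reaches only about 44% (median 500) or 37% (median 800). Power is used here only as a yardstick for precision.

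**The case against.** The strongest objection is that the protocol never says normal means the entry cut-off, and every distribution behind the 6-30% is assumed. Both statements are true. The cut-off reading is a fair inference, since no other limit is given, but it remains an inference. What the text itself shows is a missing limit and no restriction to markers raised at entry.

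A reader might infer that chance crossings inflate remission in every arm, or favour ECS. Neither follows. All arms receive prednisone and CS is a concurrent randomized control. In Step 3 the ECS rate stays near 50% because noise creates false non-responders as well as false responders; only the CS rate rises, and the difference shrinks.

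A reader might also apply the 30% directly. With assumed true rates of 40% and 60%, (1 − 0.30) × 20 = 14 points, and the sample for 80% power goes from 97 to 182 per arm. That carries a no-change rate into patients with a real effect and lets noise work in one direction only.

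It can fairly be said that most of the power gap comes from dichotomising in general, not from coincident cut-offs, and that the plan already allows means or medians and t or Mann-Whitney tests. Both stand. The unadjusted tests nevertheless give up part of the gain available from a baseline that is already measured.

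Two extensions do not stand. Requiring a 50% fall as well is arbitrary and moves the difference only from 18.9 to 19.5 points at log SD 0.5. Transit already has a stated limit and a baseline restriction, and a caveat there would change no result.

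**Conclusion.** The point holds as a matter of definition and efficiency. Item 3 is under-specified: it has no limit and, as worded, may count a marker that was normal throughout. A yes/no result on one sample is also a poor effect-size measure for planning.

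Chance crossing of about 6-30% is an illustration under no true change, and depends on the assumed distributions and on the entry cut-off being the limit. With a real effect, the shrinkage in the assumed scenario is about 1-5 points, which a pilot with a half-width of roughly 24 points could not detect. The precision lost by dichotomising is larger, and it can be recovered from planned samples. Severity is low to moderate, because this is one of ten secondary outcomes in a pilot.

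**What to change.** In secondary outcome 3 and the statistical analysis section, make the planning effect size the ECS-CS comparison of week-6 log CRP and log calprotectin, each adjusted for the patient's own baseline log value and reported as a ratio of geometric means with 95% CI. Name the baseline sample for each marker: the screening blood is the only scheduled pre-treatment CRP, and visit 2 lists the baseline stool.

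Keep biochemical remission as a supportive endpoint. State the numeric limit for each marker with its unit, count it only for the marker or markers raised at entry, and replace the either and/or wording with one rule for patients who enter with both raised.

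No new samples or visits are needed. The cost is slightly more analysis work and possibly lower reported remission percentages.

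### The only transit endpoint is a one-sided yes/no result in a baseline subset of unknown size, and the day the capsule is taken is not stated

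*Combined protocol and SAP*

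**What the plan says.** Item 5 of the secondary outcomes in the combined protocol and SAP is "Normalization of colonic transit (SHAPE 0-5 markers at day 5"), restricted to patients "among those with altered transit at baseline". The section on measurements before and after treatment gives the cut-off: "≥ 6 markers indicate delayed transit, therefore ≤ 5 is normalization of colonic transit". There is no lower limit and no earlier film, and altered transit is not defined other than as delay. Orocecal transit is listed there as a measurement, but no endpoint uses it.

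For the procedure, the "patient will take one capsule and have an x ray on day five". The study design section places the baseline test at visit 2, where randomisation occurs: "In addition, we will perform a SHAPE study and patients will be assessed by a dietitian". Its next instruction to patients is "Patients will be instructed to take the allocated treatment". At visit 3, six weeks later, the text reads "SHAPE study performed. Patients will be instructed to stop the EEN". The capsule day relative to either visit is not given.

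Hypothesis 3 predicts a beneficial change in gastrointestinal transit, and the general aim promises effect estimates with confidence intervals for all measures of interest. The statistical analysis section ties no method to the transit endpoint.

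**The concern.** Item 5 is the only endpoint that addresses the transit part of hypothesis 3. As defined, it sees one kind of change, from delayed to not delayed, in one kind of patient. The protocol introduces Crohn's disease as a condition with diarrhoea, yet a patient at the fast end of the range is scored normal at entry and cannot contribute. Nor can a patient whose transit becomes delayed on treatment, so the endpoint is blind to worsening among those who start at 5 markers or fewer. Marker counts obtained from those patients do not enter the endpoint, although its purpose is to supply an effect estimate for a larger trial.

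Timing is a separate matter. A day-five film needs a capsule taken about five days earlier. If the capsule is taken at the visit, neither film describes the period it is meant to describe, and the baseline film decides who is in the analysis.

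**Working it through.** **Inputs.** Cut-off: 0-5 normal, 6 or more delayed (item 5; measurements section). Arm size: 30 in each of three arms, 100 recruited, 10% dropout (participants section). Share with delay at baseline: not in the documents, so it is varied as an assumption.

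**1. The plan's own figure.** 3 × 30 = 90, and 90 / (1 − 0.10) = 100; equally, 90 + 10 = 100. The stated total reproduces. It rests on a pilot convention, and the transit endpoint has no sample size of its own.

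**2. What the rule can register.**

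| Markers at baseline | Markers at follow-up | Contribution to item 5 |
|---|---|---|
| 6 or more | 0-5 | counted, normalised |
| 6 or more | 6 or more | counted, not normalised |
| 0-5 | 6 or more | outside the subset; new delay not counted |
| 0-5, including any rapid transit | 0-5 | outside the subset |

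Reading altered transit to include rapid transit does not help: such a patient already meets the definition of normalisation before treatment.

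**3. Precision in the subset.** With n per arm = 30 × assumed share, the Wald 95% half-width for a difference in two proportions at p = 0.5 is 1.96 × √(0.25/n + 0.25/n) = 1.96 × √(0.5/n).

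| Assumed share with delay | n per arm | Half-width (percentage points) |
|---|---|---|
| 20% | 6 | 57 |
| 30% | 9 | 46 |
| 50% | 15 | 36 |
| 70% | 21 | 30 |
| whole arm, for reference | 30 | 25 |

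The value p = 0.5 gives the widest interval, and the normal approximation is rough at 6 to 9 per arm.

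For the marker count treated as a continuous measure in 30 per arm, the half-width is 1.96 × √(2/30) = 0.51 SD before any gain from baseline adjustment. That is on a different scale from percentage points and is not a direct comparison with the table.

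**4. Timing, under the two possible capsule days.**

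- *Capsule five days before each visit:* the film falls on the visit day, and both measurements are in the right window.
- *Capsule at visit 2, treatment started at once:* the baseline film falls about 5 days into treatment. By then the two enteral nutrition arms are on formula only, while the corticosteroid arm is on its regular diet (intervention section). If either affects transit within those days, membership of the subset depends on allocation, and the baseline count is no longer a pre-treatment covariate.
- *Capsule at visit 3:* the follow-up film falls after exclusive feeding has ended. The food reintroduction appendix gives stage 1 two days and stage 2 five days, both on half formula (2 + 5 = 7 days), so day 5 falls within partial formula plus food.

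**The case against.** Normalisation has meaning only in patients who are abnormal at the start. A subset fixed before treatment keeps the randomised comparison and costs only precision, and low precision on a mechanistic secondary endpoint is expected in a pilot. SHAPE is described at both visits without limiting it to patients with delay, and the general aim covers all measures of interest, so nothing stops the investigators from reporting the count in everyone. All of this stands, but it does not answer the point: the plan names no such analysis, and the endpoint it does name leaves those counts out.

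Four stronger readings are tempting, and the documents do not support them.

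- *Most randomised patients are dropped.* This is true only if fewer than half have 6 or more markers at baseline, that is, fewer than 15 of 30 per arm. No share is given. The exclusion also concerns this endpoint alone.
- *The endpoint misses the change that matters most in this population.* The protocol mentions diarrhoea as a feature of the disease. It does not say that these patients have rapid colonic transit.
- *Both films are contaminated.* Visit 2 is labelled pre-treatment, and an earlier capsule is not ruled out. The problem arises only if the capsule is taken at the visit and, for the baseline film, treatment starts at once. Formula is also withdrawn gradually, so patients filmed five days after visit 3 would still be on half formula.
- *Analysing everyone cures the blindness to rapid transit.* It does not. A patient near zero markers at both visits shows no change on a day-5 count under any model.

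**Conclusion.** The concern holds in a limited form. From the text alone, with no assumption, rapid transit cannot register, new delay is never counted, and patients without altered transit at baseline do not contribute to the only transit endpoint. How many patients that removes is unknown. Across assumed shares of 20% to 70% with delay, the half-width runs from about 57 down to 30 points, against 25 with the whole arm, so precision is lost throughout that range and severely at its lower end.

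The timing risk is real but conditional on an unstated capsule day. If the baseline film does follow the start of treatment, the loss goes beyond precision, because selection into the subset would then occur after randomisation. As this is a secondary endpoint in a pilot, the point is worth correcting but does not threaten the trial's main comparison.

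**What to change.** 1. Make the between-arm transit analysis the day-5 retained marker count in all randomised patients, with the baseline count as covariate, in an ordinal or count model.
2. Keep normalisation among patients with 6 or more markers at baseline as a descriptive result, and define altered transit as 6 or more markers.
3. State that a day-5 count does not assess rapid transit. Item 1 does not remove this limit.
4. State the capsule and film days so that the baseline film is taken before the first dose and the follow-up film before exclusive feeding ends, for example by giving the capsule five days before visits 2 and 3. Item 1 depends on this, since the covariate must be a true baseline value.

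The cost is protocol wording, with the same capsules and films. The capsule must be handed out ahead of each visit. Consent is already signed at screening, but eligibility is re-assessed at visit 2, so a few patients may take the capsule and then not be randomised.

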Potential mechanisms by which EEN might act include relative bowel rest, reduced antigenic load, provision of trophic amino acids, local anti-inflammatory effects, and modification of gut microbiota^{11,20}. However, there is no strong evidence to fully support any one of these mechanisms. A recent meta-analysis²⁰ showed that the effects of the therapeutic formula on specific bacterial strains were variable and inconsistent among studies, possibly due to small sample sizes and methodological limitations. Our preliminary data showed that short term dietary changes improve motility in patients with low-grade gut inflammation²¹. However, the effects of EEN on gastrointestinal transit in adults has not been yet investigated.

Evidence for the effect of EEN on quality of life, an essential patient reported outcome, is particularly scarce. Guo *et al*³⁰ found an improvement of quality of life in 13 patients with CD receiving EEN for 6 weeks. However, it is currently unknown whether EEN is more effective than CS in improving quality of life in adults with CD.

The potentially synergistic effects of adding EEN to CS therapy have not been explored before. Therefore, we designed a randomized controlled trial with the objective to investigate the effect of EEN in addition to different regimes of CS therapy (ECS) compared to CS alone (CS), for decreasing disease activity and improving quality of life in adult patients with CD. We also propose to investigate potential mechanisms underlying any beneficial effect of EEN in CD in the context of concomitant CS therapy.

Hypotheses:

- 1- Six weeks of ECS will be more effective than CS in inducing clinical remission in patients with active CD
- 2- Six weeks of EEN in addition to a short course of CS (ECSC) will have similar efficacy than ECS and reduced number of adverse events
- 3- Six weeks of ECS will lead to beneficial changes in the composition and/or metabolic activity of the intestinal microbiota, gastrointestinal transit and inflammatory burden.

Because the effect size of ECS has not been investigated before, we will perform a pilot study to assess feasibility and calculate estimates of effect size in order to plan a larger trial. Based on the significant number of patients, if the study is feasible, we will consider the sample size estimated through this pilot study for the full trial to minimize the possibility of recruiting additional patients.

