- Systemic priming to gut bacteria ([name] Lab using Flow cytometry after incubating patients' serum with cultured fecal bacteria¹⁶)
- First urine morning for metabolomics
- Intestinal permeability – indirect markers of mucosal integrity (FABP2)

Statistical analysis

There is no previous estimate on the effect of ECS compared to CS in inducing symptomatic improvement and associated changes in gut microbiota composition. Therefore, a sample size of 30 patients per arm^{28,29} should be sufficient to estimate the results and allow us to plan for future larger study. We will recruit additional 10 patients in total, to account for drop outs rates. Results will be analyzed as intention to treat (for primary outcome) and per protocol (excluding patients non-compliant with EN). The results will be expressed as n (%), mean (SD) or median (IQR) as appropriate. We will perform logistic regression to assess the association between symptomatic response and significant changes in gut microbiota composition in each group. T test or Man Whitney U test will be used as appropriate to assess differences between means. Analysis will be performed using SPSS version 21 (San Diego, CA).

Early withdrawals:

The following criteria will be considered as reasons for early discontinuation from the study (drop outs):

- Patient's decision.

- Physician's decision in case that the continuation of the patient in the study places him/her at risk.
- Patients that were not compliant with the unauthorized concomitant diets/treatments/medication will be considered as non-compliant and considered for the ITT analysis. If a subject's outcome measures worsen to the degree that they meet the study's Exclusion Criteria, study treatment will be withdrawn. Medical care will be provided as directed by the study physician and/or the subject's physician. If the required medical care conflicts with the study protocol, the subject will be placed in the intent-to-treat group. Study safety follow up will continue unless the subject withdraws, and/or is withdrawn by the study physician, and/or on the advice of the subject's physician.

Handling of adverse events

Reporting and documentation of adverse events

All adverse events occurring during the study will be reported and recorded whether or not they are considered to be non-serious, serious and/or related to the treatment. The following information will be required in each case:

- Subject and date
- Description of event
- Duration
- Frequency

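### Secondary endpoint 6 leaves open whether HAD responders or HAD scores are compared, and neither reading uses the baseline; baseline-adjusted analysis of each subscale would be more precise at no cost

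*Combined protocol and SAP*

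**What the plan says.** In the list of secondary outcomes and endpoints, introduced by "To determine the beneficial effect of 6 weeks of ECS as compared to CS in inducing", item 6 is a fall in anxiety and/or depression scores, specified in brackets as "decrease >2 points HAD-A and/or HAD-D scores". Taken literally, one subscale is enough. No minimum baseline score is set for this item, whereas item 5 limits colonic transit to patients "among those with altered transit at baseline". No inclusion criterion refers to HAD.

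The Statistical analysis section has no sentence specific to HAD. For group comparisons it says "T test or Man Whitney U test will be used as appropriate to assess differences between means". It names no test for comparing proportions between arms and no baseline adjustment. It justifies the size of the study by "a sample size of 30 patients per arm", without a power calculation. HAD is among the questionnaires listed under Measurements before and after treatment. The general aim is to estimate effects, with intervals, for every measure so that a larger trial can be planned.

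**The concern.** The endpoint is worded as a yes/no response, while the only named tests are for means. Two analysts could follow the plan and report different quantities: a difference in responder proportions, or a difference in mean scores.

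If the responder reading is used, two near-continuous scores become one binary outcome. Ordinary fluctuation on either subscale can make a responder, patients with little anxiety or depression at entry have little or no room to respond, and the size of the change is discarded. If the score reading is used, the plan still ignores the baseline value, which usually explains a good part of the variation in the follow-up score.

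The product of this pilot is a set of effect estimates for planning. A less precise HAD estimate, or one on a scale that supplies neither an SD nor a baseline correlation, serves that purpose less well.

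**Working it through.** **The plan's own figure.** The Participants section gives 100 recruited for 30 per arm after 10% dropout: 3 × 30 / (1 − 0.10) = 90 / 0.90 = 100, which reproduces. No power or sample size is stated for HAD.

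**Inputs.** From the plan: the cut of more than 2 points, either subscale, 30 per arm. The plan gives no SD, correlation, baseline level or expected effect for HAD, and no alpha. Those below are assumptions: two-sided 0.05, whole-point scores on a 0-21 scale, and the ranges shown.

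**1. Chance responders when nothing truly changes.** With whole points, a fall of more than 2 is a fall of at least 3, so the normal cut is 2.5. For one subscale, p = 1 − Φ(2.5/SD). For either subscale, the rate is 2p − P(both), where P(both) depends on the correlation r between the two changes. At SD 3 and r = 0, this is 2(0.2023) − 0.2023² = 0.364.

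| SD of change | One subscale | Either, r = 0.7 | r = 0.5 | r = 0.3 | r = 0 |
|---|---|---|---|---|---|
| 2 | 11% | 16% | 18% | 19% | 20% |
| 3 | 20% | 29% | 32% | 34% | 36% |
| 4 | 27% | 37% | 40% | 43% | 46% |

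**2. Floor.** A score of 2 or less cannot fall by more than 2. Under an either rule, only a patient at 2 or below on both subscales is excluded from responding. With assumed baseline means (HAD-A/HAD-D) of 5/3, 7/5 and 9/7, SD 4 and correlation 0.5 to 0.7 between subscales, that is 2-22% of patients.

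**3. Power at 30 per arm.** Assumed: baseline mean 8 and SD 4 on each subscale, correlation 0.6 between baseline and week 6, cross-correlation 0.5 between subscales, and a true 2-point greater fall on both. Results are from simulation with scores rounded and bounded to 0-21; hand approximations are shown as a check.

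- Either rule: 37% vs 60% respond. Pooled proportion 0.485; SE = √(2 × 0.485 × 0.515 / 30) = 0.129; 0.23/0.129 = 1.78; Φ(1.78 − 1.96) = 0.43. Simulated: about 45% (41-49% for cross-correlation 0.7 to 0.3).
- Unadjusted t test on change, one subscale: SD = 4√(2(1 − 0.6)) = 3.58; SE = 3.58√(2/30) = 0.92; 2/0.92 = 2.17; Φ(0.21) = 0.58. Simulated: 55%.
- ANCOVA, one subscale: residual SD = 4√(1 − 0.6²) = 3.2; SE = 3.2√(2/30) = 0.83; 2/0.83 = 2.41; Φ(0.45) = 0.67. Simulated: 64%.

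For the two score analyses, the simulated values are a little below the approximations because of the floor and the t distribution. The gap from either rule to ANCOVA is 64 − 45 = 19 points: 10 from dichotomising (55 − 45) and 9 from ignoring baseline (64 − 55).

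**4. If only one subscale moves.** The either rule gives about 37% vs 51%. Pooled 0.44; SE = 0.128; 0.14/0.128 = 1.09; Φ(−0.87) = 0.19. Simulated: about 20%, against about 35% for a responder rule on the affected subscale alone and 64% for ANCOVA on it.

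**5. Precision of a responder difference.** With proportions near 35% and 30 per arm, the 95% half-width is 1.96√(2 × 0.35 × 0.65 / 30) = 0.24, or 24 percentage points.

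**The case against.** The best defence is that a continuous analysis may already be intended. Item 6 speaks of a decrease in scores, with the 2-point figure only in brackets. The tests named are for means, results may be summarised as means or medians, and the and/or may mean that each subscale is looked at rather than that they form one composite. That reading is possible and the documents do not exclude it. They do not state it either, and it would still leave the comparison unadjusted for baseline. Ambiguity is therefore part of the point.

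The study is also a pilot with no power claim for HAD, and this is one of ten secondary outcomes. A responder threshold is a legitimate form of endpoint, and the scores remain available for later analysis. This stands, and it limits the importance of the point. It does not remove it, because estimation is the pilot's stated purpose.

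A reader might infer more than the plan supports:

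- That chance responders bias the comparison. They arise in every arm and do not by themselves favour one.
- That having two chances to respond always dilutes the difference. When both subscales improve, the either rule does better than a single-subscale responder rule: a 23-point difference (37% vs 60%) against 19 (24% vs 43%), with power of 45% against about 34%. Dilution occurs when only one subscale moves.
- That low scorers cannot respond. A patient low on one subscale can still respond on the other.
- That the definition costs about 30 points of power. That sets ANCOVA (64%) against a single-subscale responder rule (about 34%), which is not the rule in the plan. For the plan's rule the gap is about 19 points.

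**Conclusion.** The point holds as a gap in specification and an avoidable loss of precision, not as an error that invalidates the comparison. The plan does not say whether HAD responders or HAD scores are compared, and it uses the baseline in neither case.

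The wording of the endpoint, the missing baseline minimum, the missing adjustment and the floor for patients at 2 or below on both subscales rest on the text and arithmetic alone. Every size is conditional on assumed HAD variability, correlations, baseline levels and effect. The direction, with ANCOVA ahead of the responder rule, was the same throughout the ranges tried. For example, in simulations with the three lower to higher baseline levels above, baseline correlation 0.6 or 0.8 and effects of 1.5 to 2 points, responder power was 0.18-0.69 and ANCOVA on HAD-A 0.39-0.87. Severity is low: a worthwhile refinement of a secondary outcome.

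**What to change.** In the Statistical analysis section, state that the main HAD analysis compares the week-6 HAD-A score and the week-6 HAD-D score between ECS and CS. Analyse each subscale separately by ANCOVA adjusted for its own baseline and the randomisation stratum, and report the mean difference with its 95% CI. Report also the SD and the baseline to week-6 correlation, which the larger trial will need.

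Keep the fall of more than 2 points as a descriptive summary, given per subscale and limited to patients whose baseline on that subscale is at least 3. Reword item 6 to match.

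The cost is a few sentences of analysis wording. HAD is already collected before and after treatment, so no visit, questionnaire or patient is added.
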